10. Clinical laboratory tests will include hematology, chemistry, and urinalysis at Visits 1, 10, 13, 17, 20, 21, and 22. Clinical laboratory tests will include only ALT, AST, ALP, and TBL at all other visits indicated. Clinical laboratory tests will be collected at Visits 23 and 24 only if results from previous visits were abnormal and clinically significant. Conjugated bilirubin is required only at Visit 1.
11. Pregnancy tests are required only for females of childbearing potential. Serum pregnancy test is required at Visit 1 (sent to central laboratory). Urine pregnancy test is required for subsequent visits. A negative pregnancy test result must be obtained before the administration of the study drug.

12. Urine dipstick drug test to screen for amphetamines, cannabinoids, cocaine, and opioids. Urine drug screen at visits 1 and 3 is done for De Novo subjects only. Urine drug screen at visit 4 is done for Rollover subjects only. No urine drug screen will be conducted at visits 5, 6,7,8 and 9. Rollover Subjects will have urine collected for testing at central lab rather than being tested onsite. Opioids will not be tested for Rollover Subjects at Visits 1 and 3. De Novo Subjects on non-opioid analgesics at the time of Visit 1 must have a negative urine drug screen at Visit 1 and Visit 3. De Novo subjects on opioid analgesics at the time of Visit 1 must have a negative urine drug screen for all drugs except opioids. Dipstick urine drug screen tests will be provided by the sponsor.
13. The electronic Columbia-Suicide Severity Rating Scale (eC-SSRS) is a subject self-report rating scale (i.e., the subject completes the scale) to lifetime and study-defined suicidal ideation and to assess suicidal ideation and behaviors since the time of the last visit. Subjects who answered YES to Question 4 or Question 5 within the past 12 months of the Baseline/Screening version of the eC-SSRS (Visit 1) are not eligible to participate in this study
14. De Novo subjects taking opioid analgesics will begin to taper their opioids over the next 7-14 days. Subjects must be on ≤ 30 morphine sulfate equivalents (MSE)/day for at least 3 days before proceeding to Visit 3.
15. The modified Brief Pain Inventory-Short Form (mBPI-SF) is a subject self-report rating (i.e., the subject completes the rating inventory) of pain and the impact of that pain on daily function.

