6.5 Monitoring of Hepatic Transaminases

Hepatic function testing (alanine aminotransferase [ALT], aspartate aminotransferase [AST], alkaline phosphatase [ALP], and total bilirubin [TBL]) will be performed according to the Schedule of Assessments (Section 1.2). In the event that an elevation of ALT or AST > 3 X ULN is observed in an individual study subject, the subject should be contacted immediately and the procedures in Table 1 should be followed. The Medical Monitor or

designee may be contacted for further discussion as needed. If a subject's study drug is interrupted for 3 days or more due to elevated hepatic transaminase levels, sponsor **must** be consulted prior to restarting study drug.

Table 1: Recommended Procedures for Subjects with Elevated Aminotransferase Test Results

Magnitude of Elevation in ALT or AST	Recommendation
> 3 to ≤ 8 X ULN	The subject should be seen for an unscheduled visit as soon as possible. At the unscheduled visit, the subject will be examined for clinical signs and/or symptoms of hepatic dysfunction [fatigue, nausea, vomiting, right upper quadrant pain or tenderness, fever, rash, and/or eosinophilia (> 5%)]. Repeat hepatic function tests should be performed. Review the subject's current list of concomitant medications to assess for confounding medications that could cause elevations in AST and/or ALT. The subject should return every 48 to 72 hours for examination and repeat hepatic function testing until all test values are ≤ 2.0 X ULN or return to baseline.
> 3 X ULN and hyperbilirubinemia (> 1.5 X ULN)	Study medication should be permanently discontinued.
> 3 X ULN with ongoing, unresolved symptoms such as fatigue, nausea, vomiting, right upper quadrant pain or tenderness, fever, rash or eosinophilia (> 5%)	Study medication should be permanently discontinued.
> 5 X ULN for ≥ 2 weeks	Study medication should be permanently discontinued.
> 8 X ULN	Study medication should be permanently discontinued.

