10.3 Clinical Laboratory Tests

Clinical laboratory tests will be conducted according to the Schedule of Assessments (Section 1.2). Clinical laboratory tests will be performed by a designated central laboratory. Each site will be provided instructions for specimen collection, processing, storage, packaging and shipment. Results of laboratory tests will be provided to the site.

Clinical laboratory test data will be reviewed by the Investigator or qualified sub-Investigator. Additional clinical laboratory tests may be ordered at the Investigator's or qualified sub-Investigator's discretion. All additional testing will be performed by the designated central laboratory.

The Investigator or qualified sub-Investigator will review all lab results for clinical significance. Any laboratory result deemed clinically significant will be recorded as an AE as described in Section 10.1.

Clinical laboratory tests that will be conducted for this study are listed in [Table 3](#).

Table 3: Clinical Laboratory Tests

Hematology	Chemistry	Urinalysis

 • Hemoglobin • Hematocrit • Red blood cells • White blood cells • Platelet count • Neutrophils (absolute) • Lymphocytes (absolute) • Monocytes (absolute) • Eosinophils (absolute) • Basophils (absolute) • Mean corpuscular volume • Mean corpuscular hemoglobin • Mean corpuscular hemoglobin concentration 	
 • AST • ALT • ALP • Gamma-glutamyl transferase (GGT) • Albumin • Creatinine • Glucose • Total protein • TBL • Conjugated bilirubin • Sodium • Potassium • Chloride • CO₂ content or bicarbonate • Blood urea nitrogen 	
 • Specific gravity • pH • Glucose • Protein • Bilirubin • Ketones • Leukocytes • Blood 
For positive protein, white blood cell or blood, a microscopic examination will include the following:
 
 • Red blood cells • White blood cells • Epithelial cells • Bacteria • Crystals • Casts

Abbreviations: AST; alanine aminotransferase; ALT, aspartate aminotransferase; ALP, alkaline phosphatase; CO₂, carbon dioxide; TBL, total bilirubin.

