11.9.3 Adverse Events

Adverse events will be coded by system organ class (SOC) and preferred term using the Medical Dictionary for Regulatory Activities (MedDRA), version 17.1 or later. The incidence of treatment emergent adverse events (TEAEs) will be presented by severity and relationship to study drug as perceived by the Investigator.

Adverse events, serious adverse events (SAEs), AEs by intensity, AEs by causality, AEs leading to death, and AEs leading to study discontinuation will be tabulated by System Organ Class and Preferred Term.

The event rate (per 100 patient years) of TEAEs by preferred term will be calculated and summarized descriptively. The relationship between drug exposure and the frequency and severity of AEs will be examined.

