7.4 Definition of Visit Window

Deviations are to be expected between subjects in the actual number of study days from Day 1 to when planned visits are carried out. To handle this for tables, figures, listings, and analyses where data are to be grouped by visit, visit numbers will be defined according to [Table 1](#).

The following windows will apply only for summaries for value and change value by visit and summaries for abnormalities. If multiple assessments were performed within the visit window, the following will be applied:

- If there are multiple records in the same visit window, the measurement closest to the scheduled visit day will be used.
- If two visits are equidistant from the scheduled day, the later will be assigned to the visit.
- In the summaries for abnormalities, the worst case will be summarized for that visit regardless of how close to the scheduled visit it is.

Table 1: Windowed Visits for Summary

Visit	Scheduled Study Day	Windowed Visits for Labs	Windowed Visits for Vital Signs	Windowed Visits for ECG	Windowed Visits for CSSRS	Windowed Visits for mBPI	Windowed Visits for COWS
Baseline	First dose	<=first dose date	<=first dose date	<=first dose date	<=first dose date	<=first dose date	<=first dose date
The Titration visits		go with the actual visit	go with the actual visit	NA	NA	go with the actual visit	NA
Visit 10 - Stable Dose	1	Day 1	Day 1	Day 1	Day 1	Day 1	NA
Visit 11	30	Day2 to 45	NA	NA	NA	Day2 to 45	NA
Visit 12	60	Day46 to 75	NA	NA	NA	Day46to 75	NA
Visit 13	90	Day76 to 105	Day2 to 105	Day2 to 105	Day2 to 105	Day76 to 105	NA
Visit 14	120	NA	NA	NA	NA	Day106 to 135	NA
Visit 15	150	NA	NA	NA	NA	Day136 to 165	NA
Visit 16	180	NA	NA	NA	NA	Day165 to 195	NA
Visit 17	210	Day106 to 225	Day106 to 225	Day106 to 225	Day106 to 225	Day196 to 225	NA
Visit 18	240	NA	NA	NA	NA	Day226 to 255	NA
Visit 19	270	NA	NA	NA	NA	Day256 to 285	NA
Visit 20	300	Day226 to one day before visit 21	Day226 to one day before visit 21	Day226 to one day before visit 21	Day226 to one day before visit 21	Day286 to one day before visit 21	NA
Visit 21	357 from Titration Day 1	go with the actual visit	NA	NA	go with the actual visit	go with the actual visit	go with the actual visit
Visit 22	364 from Titration Day 1	go with the actual visit	go with the actual visit	go with the actual visit	go with the actual visit	go with the actual visit	go with the actual visit

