8.2 Protocol Deviations

Subjects with major protocol deviations and violations will be listed and summarized by the highest dose level which a subject was titrated to and for each study site and for overall subjects. Major protocol deviations or violations may include but not limited to the followings:

Subjects who entered the study even though they did not satisfy the entry criteria;

1. Subjects who developed withdrawal criteria during the study but were not withdrawn from study medication;
2. Subjects who received prohibited medication.

Subjects with one or more protocol deviations or violations in the same category/type will be counted once for that category.

Protocol deviations and violations will be captured by searching relevant data fields reported in the clinical database using computer algorithms and site monitoring by clinical research associates. All deviations and violations will be reviewed by medical monitors. Final determination of major deviations and violations will be reviewed by the study team at regular intervals throughout the trial (including the clinical study manager, the Medical Monitor, and the statistician).

Subjects who have protocol deviation/violation will also be presented in a data listing.

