8.7.5 Clinical Laboratory Evaluations

All clinical laboratory results and change from baseline values will be summarized descriptively by treatment arm. Change from baseline via -categorical variable indicating whether the individual values are inside or outside the lab normal ranges will be tabulated using shift tables.

In addition to change from baseline summaries, hepatic function results (alanine aminotransferase [ALT], aspartate aminotransferase [AST], alkaline phosphatase [ALP], and total bilirubin [TBL]) will be summarized by treatment arm for an elevation of ALT or AST >1 to ≤ 3 X ULN; > 3 to ≤ 5 X ULN, and > 5 to ≤ 8 X ULN.

Individual results that are outside of normal range will be flagged in data listings.

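### The SAP's graded liver table stops at 8 × ULN and sets no bilirubin cut-off, so no planned table counts two of the protocol's hepatic discontinuation criteria

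*SAP*

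**What the plan says.** **SAP 8.7.5** plans one hepatic summary graded against the upper limit of normal (ULN). The ALT/AST categories are above 1 up to 3 × ULN, followed by "> 3 to ≤ 5 X ULN, and > 5 to ≤ 8 X ULN". The sentence also names ALP and TBL among the hepatic results, but gives cut-offs only for ALT or AST. Results are to be shown by treatment arm. The rest of 8.7.5 consists of descriptive statistics, normal-range shift tables and flagged listings. Protocol 11.9.4 adds no graded hepatic table.

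**SAP 7.4** says how several values in one visit window are handled: "In the summaries for abnormalities, the worst case will be summarized for that visit".

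**Protocol 6.5, Table 1** gives four situations in which study drug is stopped permanently. One is ALT or AST above 8 × ULN. Another is "> 3 X ULN and hyperbilirubinemia (> 1.5 X ULN"). The other two are "> 5 X ULN for ≥ 2 weeks" and a rise above 3 × ULN with unresolved symptoms. For values above 3 and up to 8 × ULN, Table 1 asks for an unscheduled visit and retesting every 48 to 72 hours.

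**Protocol 1.2, footnote 10** describes the reduced panel: "Clinical laboratory tests will include only ALT, AST, ALP, and TBL at all other visits indicated". The full chemistry panel in Protocol 10.3, Table 3, also contains ALT, AST and TBL.

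**The concern.** Long-term safety is the primary objective, and laboratory evaluations are among the key safety endpoints. A graded liver table is where a reader looks for the most extreme transaminase values, and for transaminase rises accompanied by raised bilirubin. This one closes its top category exactly where the protocol's magnitude-only stopping criterion begins, and it defines no joint category.

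The closed top looks like an oversight. Other graded scales in the SAP are open-ended: COWS ends with a category above 36, exposure with more than 13 months, and QTc with more than 500 ms. The last of these matches the protocol's QTcF interruption threshold of 500 msec. The hepatic criteria have no equivalent row.

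At stake is whether the study report can state, from a planned table, how many subjects met either criterion, including a clear statement if none did.

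**Working it through.** There is no planned figure to reproduce. The check places values in the SAP bands and compares the result with Table 1.

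**1. Band check.** The bands are (1, 3], (3, 5] and (5, 8]. The test values are illustrative, in × ULN.

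| ALT or AST | TBL | SAP band | Above 8 × ULN? | Above 3 with TBL above 1.5? |
|---|---|---|---|---|
| 4 | 1.0 | (3, 5] | no | no |
| 4 | 2.5 | (3, 5] | no | **yes** |
| 6 | 1.0 | (5, 8] | no | no |
| 6 | 2.5 | (5, 8] | no | **yes** |
| 8 | 1.0 | (5, 8] | no | no |
| 8.1 | 1.0 | none | **yes** | no |
| 12 | 1.0 | none | **yes** | no |
| 12 | 3.0 | none | **yes** | **yes** |

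None of the three bands holds a value above 8 × ULN. Subjects with and without the joint criterion share a cell.

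**2. Worst-case rule.** In SAP Table 1 the laboratory window for Visit 17 runs from Day 106 to Day 225, which is 225 − 106 + 1 = 120 days. Retesting every 48 to 72 hours can put several samples in one window. Suppose a subject has 4 × ULN and then 9 × ULN in that window. With the first value alone, the subject counts in (3, 5] for Visit 17. With both, 9 represents the visit and the subject is in no band. The subject may still appear in a lower band at another visit.

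**3. Other planned outputs.**

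| Output | What it can show | Why it is not a count by criterion |
|---|---|---|
| Flagged listings (SAP 8.7.5) | every value outside the normal range | a listing, not a tabulated count |
| Shift tables (SAP 8.7.5) | movement into or out of the normal range | not graded |
| Descriptive statistics (SAP 7.1, 8.7.5) | a maximum per visit | no number of subjects; SAP 7.4 uses the record nearest the scheduled day, so an unscheduled peak can be missed |
| Adverse events (Protocol 10.3: "Any laboratory result deemed clinically significant will be recorded as an AE") | clinically significant results | depends on the investigator's judgement; summarised by term, not by threshold |
| Discontinuations (Protocol 11.9.3: "AEs leading to study discontinuation will be tabulated by System Organ Class and Preferred Term") | subjects stopped for a liver event | by term, not by threshold |
| Deviations (SAP 8.2: "Subjects who developed withdrawal criteria during the study but were not withdrawn from study medication") | subjects who should have stopped and did not | leaves out those stopped correctly; not by hepatic criterion |

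**4. Pairing ALT/AST with TBL.** Two illustrative subjects show why a joint row needs a rule.

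- Subject A has ALT 4 and TBL 0.8 on Day 30, then ALT 1.2 and TBL 1.8 on Day 300. Independent worst values give (4, 1.8), a joint case built from two unrelated peaks.
- Subject B has ALT 4 and TBL 1.0 at one draw. At a retest 72 hours later TBL is 2.0 but ALT is no longer above 3. Same-sample pairing misses this subject, although both values belong to one episode.

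**5. Scale.** The documents give no rate, so the rates here are assumptions, with N = 600 from Protocol 11.2. The chance of at least one affected subject is 1 − (1 − p)^600.

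| Assumed true rate p | Chance of at least one in 600 |
|---|---|
| 0.05% | 26% |
| 0.1% | 45% |
| 0.2% | 70% |
| 0.5% | 95% |

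If a planned row showed 0 of 600, the one-sided 95% upper bound would be 1 − 0.05^(1/600) = 0.50%. As written, the plan has no row in which to report that zero.

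**The case against.** **Table 1 guides clinical management.** It is headed as recommended procedures, and Protocol 11.9.4 asks for no graded hepatic table, so the SAP already goes beyond the protocol. This stands. A reader might infer that the SAP contradicts the protocol, but it does not. The point is that a table the SAP chose to include is incomplete at its upper end.

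**TBL may be covered.** The SAP sentence lists TBL and then says the hepatic results are summarised for ALT or AST elevations. It can fairly be read as describing TBL within each band. This stands in part: it is too strong to say that the plan ignores bilirubin in subjects with raised transaminases. Even on that reading there is no 1.5 × ULN cut-off, hence no joint count, and values above 8 × ULN still have no band.

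**Extreme values will be seen anyway.** They are flagged in listings and may appear as maxima, adverse events or deviations. With a handful of cases a reader could count from the listing, and both documents allow further analyses. This limits the harm. It does not supply a pre-specified count for a primary safety question.

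**By visit, not by subject.** The wording of SAP 7.4 points to a by-visit display. This stands, and it rules out a fixed figure for how far any count above 3 × ULN falls short.

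**Conclusion.** The concern holds as a gap in reporting. The missing category above 8 × ULN is plain from the text and rests on no assumption. The missing joint count also holds, whichever way the TBL wording is read, because no TBL cut-off is given.

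The number of subjects affected is unknown and may be zero; the rates used above are assumptions for scale only. Two stronger inferences are not supported:

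- **Severe liver findings would be lost or hidden.** They would not: the data are collected, and the values outside the normal range are listed.
- **The table should have counted all four Table 1 criteria.** The duration and symptom criteria have no dedicated count either, but they need information on persistence or symptoms that ALT/AST and TBL thresholds do not carry. This point covers only the two criteria defined by laboratory thresholds.

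The change is worth making before the analysis. No view is taken on the clinical stopping rules.

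**What to change.** In SAP 8.7.5:

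1. **Open the top.** Add a row for ALT or AST above 8 × ULN, or use cumulative rows above 3, 5 and 8 × ULN. Count each subject once by worst post-baseline ALT or AST, including titration and unscheduled visits, in addition to any by-visit display.
2. **Add a joint row.** Count subjects with ALT or AST above 3 × ULN and TBL above 1.5 × ULN, using the protocol's existing thresholds. Table 1 does not say whether both values must come from one sample. The SAP should therefore fix a pairing rule before the analysis that covers the same sample and repeat samples in the same elevation episode, and should define when an episode ends. Unrelated peaks are then not paired, and a later bilirubin rise in the same episode is not missed.
3. **State how TBL is summarised** within the ALT/AST bands, if that is what the sentence intends.
4. **Replace treatment arm**, since this single-drug, open-label study has none. Present De Novo, Rollover and all subjects combined, as Protocol 11.9 requires. The finer groups in SAP 7.1 are optional.

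The cost is SAP wording, one pairing definition and one table shell. ALT, AST and TBL are already measured together in both panels, so no new data are needed and no clinical rule changes.

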8.7.6 Vital Signs and ECGs

The following variables will be derived for systolic and diastolic supine blood pressure and supine pulse rate and/or ECG parameters:

- Change from baseline.
- Treatment-emergent change from baseline, see [Appendix 1](#) (treatment-emergent decrease/increase).
- Categorical variable indicates whether the individual values are inside or outside the predefined clinical relevant ranges.
- Overall interpretation of ECGs as normal or abnormal will be recorded at the visits as specified in the assessment schedule.

Descriptive statistics will be presented for scheduled visits on observed data. In addition to the descriptive statistics, treatment-emergent abnormal value and shifts from baseline to post-baseline result will be presented. All the summaries mentioned above will be performed by the dose level in which subjects were titrated.

Data listings with flagging for values outside normal ranges will be presented.

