6.2 Treatment Period (Visits 3-20)

At Visit 3, subjects will be evaluated for entry into the Treatment Period. The Investigator or qualified sub-Investigator will complete the COWS ([Wesson, 2003](#)). The subject must score ≤ 12 to continue in the Treatment Period. Subjects who score greater than 12 will complete their Screening Period and end study participation and will be treated appropriately for withdrawal according to the investigators clinical practice. A Rollover Subject's last COWS assessment during Study 14-181-07 or Study 14-181-12 will satisfy this requirement. De Novo Subjects will discontinue all current analgesics including their prior opioid medication.

All subjects will begin dosing with 100-mg NKTR-181 BID with dose escalation in stepwise increments of 100-mg (e.g., from 200-mg BID to 300-mg BID) up to a maximum dose of 600-mg BID. All dose escalations will occur prior to visit 10. The dose of NKTR-181 will not exceed 600 mg BID in this study. Subjects will be instructed to take study drug BID, preferably at 8 AM and 8 PM. Subjects will also receive training on the recognition and management of constipation and other opioid related side effects. Side effects should be managed according to standard of care practices.

If a subject cannot tolerate 100-mg NKTR-181 BID, the subject will be discontinued from the study; these subjects will be required to complete the Early Termination (ET) visit (Visit 21/ET) and safety follow-up requirements. Refer to the Schedule of Assessments (Section 1.2) for complete information regarding all assessments to be completed at the ET Visit and safety follow-up requirements.

Within 4-10 days after receiving the first dose of NKTR-181, subjects will return to the clinic at which time the Investigator will assess for tolerability and effectiveness. **Tolerability** and **effectiveness** will be assessed based on Investigator (or qualified sub-Investigator) clinical judgment. The Investigator (or qualified sub-Investigator) will determine whether the subject should remain at the current dose or titrate to the next dose level.

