Subjects will return to the clinic for assessments of tolerability and effectiveness every 4 to 10 days for up to 6 more times over a 5-week period until a stable dose is achieved. A **stable** dose is a dose that is effective and tolerated on two sequential visits (i.e., after at least 8 days of continuous treatment). Subjects who continue to tolerate study drug but do not have adequate relief of pain, based on the Investigator's clinical judgment, will continue dose escalations of 100-mg BID increments until the maximum dose of 600-mg NKTR-181 BID is reached.

Subjects who do not achieve adequate pain control at 600-mg NKTR-181 BID will be classified as non-responders and will be discontinued from further participation in the study.

Non-responders will be required to complete the ET Visit (Visit 21/ET) and safety follow-up requirements.

Subjects will begin a monthly clinic visit schedule after a tolerable, effective and stable dose is achieved. **Doses of NKTR-181 may be adjusted upwards (up to a maximum dose of 600-mg NKTR-181 BID) or downwards as needed during the Treatment Period, based on the Investigator's (or qualified sub-Investigator's) assessment of effectiveness and tolerability.**

If at any time a subject cannot tolerate study drug between protocol-mandated visits, per Investigator discretion, an unscheduled visit should occur. For subjects with tolerability issues, the dose of NKTR-181 may be adjusted downwards, as necessary, based on the Investigator's clinical judgment in a stepwise 100-mg changes (e.g., 300-mg BID may be lowered to 200-mg BID). Dose adjustments may occur at unscheduled visits, however, an unscheduled visit will not replace a regularly scheduled visit, and the subject should be seen at all regularly scheduled visits.

Throughout the Treatment Period, subjects who experience breakthrough pain will be allowed rescue medication, as outlined in Section 6.4. Note: If subject is off of study drug for 3 days or more, sponsor **must** be consulted prior to restarting study drug.

Subjects will report their pain experience at each visit using the mBPI-SF. At quarterly intervals, subjects will be assessed for vital signs, 12-lead electrocardiogram (ECG), and clinical laboratory testing.

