8.0 STATISTICAL ANALYSES

8.1 Subject Disposition

Frequency counts and percentages will be tabulated for all subjects who complete or early discontinue from the study drug. Reasons for early discontinuation from study drug will be summarized by the highest titrated dose level.

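### Vital signs, ECGs and reasons for discontinuation are grouped by a titrated-dose label, not by the dose being taken at the time, so dose comparisons in these tables are distorted in a direction that depends on the summary

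*SAP*

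**What the plan says.** SAP 8.7.6 covers supine blood pressure, supine pulse and ECG parameters: change from baseline, treatment-emergent change, out-of-range categories and shifts. It then fixes the grouping: "All the summaries mentioned above will be performed by the dose level in which subjects were titrated". SAP 8.1 does the same for stopping: "Reasons for early discontinuation from study drug will be summarized by the highest titrated dose level".

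The dosing rules are in Protocol 6.2:

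- Start and steps: "All subjects will begin dosing with 100-mg NKTR-181 BID with dose escalation in stepwise increments of 100-mg", to a maximum of 600 mg BID.
- Timing: "Within 4-10 days after receiving the first dose of NKTR-181, subjects will return to the clinic", and afterwards "every 4 to 10 days for up to 6 more times over a 5-week period".
- Who moves up: "Subjects who continue to tolerate study drug but do not have adequate relief of pain".
- At the top: "Subjects who do not achieve adequate pain control at 600-mg NKTR-181 BID will be classified as non-responders", and they leave the study.
- Later changes: doses may be "adjusted upwards (up to a maximum dose of 600-mg NKTR-181 BID) or downwards as needed during the Treatment Period".
- End: a one-week taper brings every subject who reaches it to 100 mg BID for at least two days before Visit 22.

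SAP 7.2 defines the stable dose as the dose at Visit 10, but 8.7.6 does not say whether its label means that dose or the highest dose reached. Protocol 11.9 plans safety summaries by De Novo, Rollover and combined, and SAP 7.1 sets entry cohort as the general grouping. The dose grouping appears only in the SAP, whose section 9.0 reports no changes from the protocol.

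**The concern.** A single label per subject does two things.

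First, it files measurements under a dose that the subject had not yet reached, or had already left. A real effect of dose on blood pressure or pulse is then blurred at those visits.

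Second, in the discontinuation table a subject must stay on drug and tolerate every lower dose to enter the 600 mg row, while anyone who stops early lands in a lower row. This is immortal time combined with selection of tolerators. It can produce a gradient across doses when none exists.

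A reader of the study report will use dose rows to judge how well 500-600 mg is tolerated compared with lower doses. The rows as defined do not support that reading.

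**Working it through.** The plan states no figure on this point and has no formal sample size, so there is nothing to reproduce. The counts below come from the Schedule of Assessments (Protocol 1.2) and SAP Table 1. The hazards are assumptions, because the documents give none.

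**1. Assessments filed under a dose not being taken**

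- Vital signs on treatment: Visits 4-9 (6), Visits 10, 13, 17 and 20 (4), and Visit 22 (1), so 11.
- ECGs on treatment: Visits 10, 13, 17, 20 and 22, so 5. None is scheduled in titration, and Table 1 marks ECG as not applicable there.
- Fastest path to 600 mg: Visits 4, 5, 6, 7, 8 and 9 are measured on 100, 200, 300, 400, 500 and 600 mg. Visit 22 is measured on 100 mg.
- Vital signs below the label: 5 + 1 = 6 of 11 (55%). ECGs: 1 of 5 (20%).
- With six titration visits and the same step-up, the vital-sign counts for labels of 200, 300, 400 and 500 mg are 2, 3, 4 and 5 of 11.
- In time the share is smaller. Five steps take at least 5 × 4 = 20 days. The first return visit by Day 10 plus the 5-week limit gives about 10 + 35 = 45 days at most. That is 20/364 = 5.5% to 45/364 = 12.4% of treatment.

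**2. Discontinuation by highest dose when dose has no effect**

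Assume a constant hazard h, equal numbers heading for each of the six doses, and steps every s days. Let S(t) = exp(−ht), and count stops to day H. For dose level j (1 = 100 mg, 6 = 600 mg), let a = S((j−1)s) and d = (6−j)[a − S(js)]. Then

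row rate = [a − S(H) + d] / [a + d].

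*15% stop within 60 days, counted to Day 60, s = 7.* h = −ln(0.85)/60 = 0.00271, S(7) = 0.9812, S(35) = 0.9096.
- 100 mg: (0.150 + 5 × 0.0188) / (1 + 5 × 0.0188) = 22.3%.
- 600 mg: (0.9096 − 0.85) / 0.9096 = 6.5%.
- All rows from 100 to 600 mg: 22.3, 19.4, 16.4, 13.3, 10.0 and 6.5%.
- With s = 4: 19.3% down to 10.3%.

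*Same hazard, counted to Day 357, s = 7.* S(357) = 0.3802.
- 100 mg: (0.6198 + 0.0939) / 1.0939 = 65.2%.
- 600 mg: (0.9096 − 0.3802) / 0.9096 = 58.2%.

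*10% stop over 357 days, s = 7.* h = −ln(0.90)/357 = 0.000295, S(7) = 0.99794, S(35) = 0.9897.
- 100 mg: (0.100 + 5 × 0.00206) / (1 + 5 × 0.00206) = 10.9%.
- 600 mg: (0.9897 − 0.90) / 0.9897 = 9.1%.

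**3. The same check by dose interval**

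Assume that 5% stop for an adverse event in each dose interval, that 70% of those remaining escalate, and that 10% of those who settle stop later.
- Every row from 100 to 500 mg: (0.05 + 0.95 × 0.30 × 0.10) / (0.05 + 0.95 × 0.30) = 23.4%.
- 600 mg: 0.05 + 0.95 × 0.10 = 14.5%.

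Now let the risk truly rise, from 3% to 8% per interval and from 8% to 13% later.
- 100 mg: (0.03 + 0.97 × 0.30 × 0.08) / (0.03 + 0.97 × 0.30) = 16.6%.
- 500 mg: (0.07 + 0.93 × 0.30 × 0.12) / (0.07 + 0.93 × 0.30) = 29.7%.
- 600 mg: 0.08 + 0.92 × 0.13 = 20.0%.

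The dose with the highest risk looks safer than the one below it.

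**4. Vital signs can go the other way**

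Suppose abnormality tables are pooled across visits and each visit has the same chance q of an abnormal value at every dose. An early stabiliser on 100 mg has 7 assessments (two titration visits, then five), and a 600 mg subject has 11. With 1 − (1 − q)^n, q = 1% gives 6.8% v 10.5%, and q = 5% gives 30.2% v 43.1%. Here the 600 mg row looks worse with no dose effect.

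**The case against.** A reader might infer that high doses are made to look better tolerated by construction. The documents do not support that as a general statement. Mean vital-sign changes are diluted, but pooled abnormality counts can run against the high dose. A subject who is reduced for intolerance and then stops is still charged to the higher dose. Non-responders at 600 mg must leave. If 15% of those remaining at 600 mg do so, in the setting of the first calculation in step 3, stops for adverse events or non-response there are 0.05 + 0.95 × (0.15 + 0.85 × 0.10) = 27.3%, against 23.4% in lower rows. SAP 8.1 tabulates reasons, so this last case can be separated from adverse-event stops, where the selection effect remains.

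Other stronger readings also fail. ECGs taken during titration cannot be misfiled, because none is scheduled. Respiratory rate is not among the variables listed in 8.7.6. The primary objective concerns the safety and tolerability of NKTR-181 and makes no comparison between doses. The 22% v 6.5% gradient should not be quoted alone, since it counts no stops after Day 60 in a 52-week study.

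The defence can add that descriptive statistics are by scheduled visit, so Visit 4 values appear as Visit 4 values, when everyone is on 100 mg, and Visits 10-20 mostly match the label. Kaplan-Meier time to discontinuation (SAP 8.6.3), event rates per 100 patient-years and an examination of exposure against adverse events (Protocol 11.9.3) are also planned. All of that stands and limits the damage. None of it specifies a summary of these values or stops by the dose in use at the time.

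**Conclusion.** The point holds in a limited form. The dose rows in SAP 8.7.6 and 8.1 are not exposure-based.

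- **Vital signs and ECGs.** At most 6 of 11 scheduled vital-sign assessments and 1 of 5 scheduled ECGs are misfiled for a 600 mg completer on the fastest path with no later dose change. Fewer vital signs are misfiled for lower labels. Later dose changes and unscheduled assessments add to this by an amount that cannot be computed from the documents. The direction depends on the summary.
- **Discontinuation for adverse events.** Selection tends to favour the top dose. Its size ranges from about 2 percentage points (10.9% v 9.1%) to about 16 (22.3% v 6.5%) across the closed-form cases. Those rest on an assumed constant hazard, equal target doses and regular steps.

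The tables are descriptive and dose is not randomised, so no formal inference is at risk. What is at risk is a misleading reading of tolerability by dose, and it is cheap to prevent.

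**What to change.** - **SAP 8.7.6:** add summaries of blood pressure, pulse and ECG values by the dose being taken at assessment, and show Visit 22 as post-taper.
- **SAP 8.1:** add discontinuations by reason and dose at stopping, per person-time on that dose. A flat hazard then shows as a flat rate.
- **SAP 8.5:** add time on each dose as the denominator.
- **Label:** state whether the titrated dose means the Visit 10 stable dose or the highest dose reached. Keep the existing tables, marked as descriptive only. Removing them is not necessary.
- **Protocol 6.2:** the statement that all escalations occur before Visit 10 and the allowance of later upward adjustment must be reconciled. The label and SAP 8.6.2, which analyses increases after Visit 10, both depend on it.

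The cost is some programming. Dosing records by dose level are already needed for cumulative dose in SAP 8.5 and time to dose increase in SAP 8.6.2. The new rows remain non-randomised and selected, since escalation depends on tolerance and pain relief, so they too should be read descriptively.
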